9.1.2 Description of Visits

Activity	Treatment Preparation	Treatment Phase				Follow up	
	V1	V2	V3	Phone Call	V4	Phone Call	V5
	Day -28	Day 1	Day 28	Day 56	Day 84	Day 140	Day 168 SVR12
Routinely assessed data required for this study							
Patient information and informed consent	X						
Inclusion/Exclusion Criteria check (Patient Selection)	X						
Demographics: Year of birth, ethnicity, sex	X						
HCV History (first diagnosis, date and source of infection, fibrosis stage)	X						
Medical History (including extrahepatic manifestation)	X						
HCV Viral load	X	X	X		X		X
Start the medication regimen		X					
Adverse events		X 	X		X		X 
Concomitant medication	X	X	X		X		X
Explain function and wearing of activity tracker	X						
Handing out the activity tracker	X						
Investigation of handling with the activity tracker		X	X		X		X
Reminder Call to start new cycle of wearing the activity tracker				X		X	
Collect activity tracker							X
FSS Questionnaire 	X	X	X		X		X

Additional data recorded in the CRF if routinely available							
Physical Exam	X				X		X
Vital signs (blood pressure, pulse, weight, height and body temp)	X	X	X		X		X
Smoking and Alcohol status	X						X
Laboratory	X	X	X		X		X
Treatment documentation (compliance)			X		X		
1: Capturing Adverse Events and Serious Adverse Events begins with the signature of the informed consent and stops 30 days after the last intake of the 3D regimen. 2: To be filled out at every visit by the patient himself and without any prior influence by the study personal.							

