**Study Design:**

This is an observational, prospective, open label, single-arm, multi-centric, real-life study in HCV-positive patients (genotype 1).

The study consists of a treatment preparation phase of 4 weeks to obtain baseline physical activity by use of a wrist-worn activity tracker, a treatment phase (12 weeks) and a follow-up phase (12 weeks) to evaluate treatment response. The activity tracker is worn for 4 weeks before each visit, to obtain stable individual activity data. At every visit, questionnaire-based fatigue is recorded (FSS questionnaire), according to routine clinical care.

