**Figure 1: Study Activities**

### 9.1.1 Description of Activities

Patients will be screened to ensure they meet the inclusion criteria. All patients will be required to sign an informed consent to use and disclose personal health information. By signing this consent, patients agree to release their information to AbbVie. No study related activity will be performed prior to obtaining written informed consent.

When the investigator has determined that the patient is eligible for participation, and the patient has agreed to be included in this observational study, the patient will be handed out his personal activity tracker (ActiGraph GT9X Link [26]) (Figure 1) and will be instructed in its use. The patient will be advised to report any potential side effects related to the activity tracker, such as possible discomfort wearing the device around the clock or possible skin rash or skin irritation, to the study personnel. ActiGraph GT9X Link has a data storage capacity of 240 days/4GB. Therefore, the patient will keep the tracker for the whole duration of the study (196 days). The patients will be requested to start wearing their activity trackers on the non-dominant arm constantly for 8 weeks between visit 1 and visit 3 and for 4 weeks preceding visits 4 and 5. Everytime the patient has to put on his tracker, he will receive a reminder call from a local study personnel to increase adherence. At the last visit, the investigator will collect the tracker and deliver it to the biostatistician which in turn transfers the activity data to a post-processed environment (ActiLife 6 [27]) (Figure 1).

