#### **11.1.4 Serious-, non Serious Adverse Event and Pregnancy Collection Period**

SAE, AE and pregnancy will be reported to AbbVie from the time the physician obtains the patient's authorization to use and disclose information (or the patient's informed consent) until 30 days or 5 half-lives following the intake of the last dose of physician-prescribed treatment, whichever period is longer.

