#### **11.1.6 Serious Adverse Event Reporting**

For events from patients using and AbbVie product - notify the AbbVie contact person identified below within 24 hours of the physician becoming aware of the event.

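### Adverse events are not asked about at the two tracker reminder calls, so the last 56 of 84 treatment days have one scheduled enquiry; asking at the calls is a cheap improvement

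*Protocol*

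**What the plan says.** The visit table in protocol section 9.1.2 places the contacts after V2 at V3 (Day 28), a call (Day 56), V4 (Day 84), a call (Day 140) and V5 (Day 168). The AE row is ticked at V2, V3, V4 and V5 and is empty in both call columns. The only row ticked for the calls is "Reminder Call to start new cycle of wearing the activity tracker". Section 9.1.1 gives the same purpose: whenever the tracker has to be put on again, the patient is phoned, that is, "he will receive a reminder call from a local study personnel to increase adherence". Neither place gives the caller the task of asking about AEs.

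Footnote 1 of the table is attached to the AE ticks at V2 and V5. It starts capture at informed consent and says that it "stops 30 days after the last intake of the 3D regimen". Section 11.1.4 describes the same period differently: "until 30 days or 5 half-lives following the intake of the last dose of physician-prescribed treatment, whichever period is longer".

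Reporting is not tied to visits. Section 11.1.5 allows five business days for AEs, and section 11.1.6 requires notification of serious events "within 24 hours of the physician becoming aware of the event". The SAP analyses safety parameters in all three populations (sections 5.1 and 5.2). Its planned table 3.2 takes AEs and serious AEs from the data of Visits 2 to 5.

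**The concern.** The reporting clocks start when the physician learns of an event. Between visits, the plan relies on the patient to volunteer it or on some other routine contact. Halfway through the treatment phase, site personnel already phone the patient, but only about the tracker. After V3 nobody is scheduled to ask about AEs for 56 days, and after V4 for 84 days.

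Two things are at stake. First, an event that nobody volunteers may reach the sponsor weeks after it happened. Second, events recalled over 8 to 12 weeks are likely to be less complete and less exactly dated. Dating matters here because capture stops a fixed time after the last dose, so a vague onset date makes it hard to say whether an event belongs in the table.

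**Working it through.** **Inputs.** Contact days and AE ticks come from the table in section 9.1.2. The phase lengths come from the Study Design paragraph of the abstract: "a treatment phase (12 weeks) and a follow-up phase (12 weeks) to evaluate treatment response". The 30-day window comes from footnote 1. The last dose is assumed to fall on Day 84 (start on Day 1, 84 days of treatment), with Days 82 to 85 as the range.

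**Reproducing the plan's own figure.** Day 168 − (Day −28) = 196 days = 28 weeks. This matches the study duration in section 9.1.1, so the day numbering is read correctly.

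**Gaps between scheduled AE enquiries as planned (Days 1, 28, 84, 168).**
- V2 to V3: 28 − 1 = 27 days
- V3 to V4: 84 − 28 = 56 days, which is 56/84 = two thirds of treatment
- V4 to V5: 168 − 84 = 84 days

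Days 29 to 83 hold no scheduled AE enquiry. Days 29 to 84 hold one, on the last day.

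**The post-dose window.** With the last dose on Day 84, the window is Days 85 to 114 (84 + 30 = 114). The next contact of any kind is the call on Day 140, 140 − 114 = 26 days after the window closes. The next AE enquiry is V5, 168 − 114 = 54 days after it closes.

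| Last dose | Window | Scheduled contact inside | Day 140 call after closing | V5 after closing |
|---|---|---|---|---|
| Day 82 | 83–112 | V4 (Day 84) | 28 days | 56 days |
| Day 83 | 84–113 | V4 (Day 84) | 27 days | 55 days |
| Day 84 | 85–114 | none | 26 days | 54 days |
| Day 85 | 86–115 | none | 25 days | 53 days |

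Where V4 does fall inside, it is on the first or second day of the window and sees almost none of it.

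**With AEs also asked about at both calls (Days 1, 28, 56, 84, 140, 168).** The gaps become 27, 28, 28, 56 and 28 days.
- Longest on-treatment gap: 56 falls to 28 days.
- Day 84 to the next enquiry: 84 falls to 56 days.
- First enquiry after the window closes: 54 falls to 26 days.
- Contacts inside Days 85 to 114: none before, none after.

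**Effect of the other window definition.** Under section 11.1.4 the window could be longer than 30 days. For the Day 140 call to fall inside it, the window would have to last at least 140 − 84 = 56 days, which means a half-life of at least 56/5 = 11.2 days. The documents give no half-life, so Day 114 holds only under footnote 1.

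**The case against.** The strongest defence is that this is a non-interventional study. Visits and procedures follow routine practice, no safety endpoint is listed among the objectives or variables, and no passage contradicts another on whether callers should ask. Active questioning at a tracker call is thus an enhancement and not the repair of an error. That stands, and it is why the point is only a cheap improvement. It does not remove the point, because the calls are themselves study-specific contacts and one question adds no visit or procedure.

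Three stronger readings are tempting, and the documents do not support them.

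- A reader might infer that events between visits go uncollected. Sections 11.1.4 to 11.1.6 require reporting throughout the collection period once the physician is aware, and the V5 tick carries footnote 1, so V5 gathers the post-dose window in retrospect. What is missing is a scheduled question, not collection.
- A reader might infer that the blank call columns are what leaves the 30-day post-dose window without contact. They are not. The second call comes 26 days after the window closes, and asking then would still leave Days 85 to 114 empty. The cause is that nothing is planned between Day 84 and Day 140.
- A reader might infer that the AE counts in SAP planned table 3.2 will be too low by some known amount. The documents give no figure for unrecalled events. Delays of 56 or 84 days are upper limits that assume the patient volunteers nothing and has no other routine contact.

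The cost is also a little more than one tick. The training described in section 9.1.1 covers the tracker and its software, so callers would need brief instruction on asking about and passing on events.

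**Conclusion.** The point holds as a cheap improvement. Two planned calls pass without an AE question, leaving one scheduled enquiry in the last 56 of 84 treatment days and 84 days until the next. The consequence is delayed and probably less complete ascertainment, of unknown size. The real gain from asking is on treatment, where the longest gap is halved from 56 to 28 days. The gain after treatment is modest: retrospective questioning 26 instead of 54 days after the 30-day window closes.

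These figures assume visits on their nominal days, a last dose on Day 84 and the 30-day limit of footnote 1. Moving the last dose by a day or two changes them by the same number of days. They describe patients who complete treatment. Under section 9.1.4, a patient who stops treatment early is withdrawn and may have no V5, so V5's retrospective capture cannot be assumed for that group.

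Separately, footnote 1 and section 11.1.4 define the end of AE collection differently and must be reconciled.

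**What to change.** 1. In the section 9.1.2 table, tick the AE row in both phone-call columns.
2. In section 9.1.1, state that the caller asks one open AE question, records the onset date of anything reported and passes it to the investigator the same day, so that the clocks in sections 11.1.5 and 11.1.6 start.
3. In SAP planned table 3.2, add the two calls as AE sources beside Visits 2 to 5.
4. Reconcile footnote 1 with section 11.1.4, so that the site, the CRF and the analysis use one end of collection.
5. State openly that the calls put no contact inside Days 85 to 114 and that events in that window rest on spontaneous reports and later recall.

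The cost is one question on at most two existing calls per patient, brief instruction for the callers, a few CRF lines and a few more non-serious events to process. No new contact or staff is needed.

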### 9.1.3 Product Supply

Commercially available 3D regimen will be used as per routine clinical practice and local label/guidelines. AbbVie will not provide the medication for this study.

### 9.1.4 Termination Criteria

A patient may withdraw from the study at any time. The investigator may discontinue any patient's participation for any reason. AbbVie AG may interrupt/stop the study at any time for any reason.

If a patient withdraws or is lost to follow-up, the reason for withdrawal will be recorded in the CRF if voluntarily shared by the patient. In case of study termination, the investigator must ensure that the patient returns the activity tracker, and that no subsequent activity tracker will be shipped to the patient.

Specifically, the following termination criteria apply:

- Patients not eligible for treatment with 3D regimen in accordance with the Swiss product label and according to the investigator's judgment will discontinue study participation.
- Patients who discontinue treatment with 3D regimen or who do not wear the activity tracker for at least 3 weeks before each visit will be withdrawn from the study. In case the decision to discontinue treatment with 3D regimen was taken before or during a routine clinic visit, this visit will be considered the last study visit. The last dose of treatment of 3D regimen will be recorded in the CRF.
- Patients with an average FSS score < 4 at visit 2 will discontinue the study.

Following discontinuation of the study, the patient will be treated in accordance with the investigator's best clinical judgment.

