If the investigator sees the medical indication to initiate treatment with 3D regimen before the patient has worn the activity tracker for at least 4 weeks during the treatment preparation phase, or if 3D regimen is discontinued at the investigator's discretion, the patient will discontinue study participation. ActiGraph GT9X Link comes with a wear time sensor that automatically detects if a wrist worn device has been removed. Thus, patient compliance to the tracker will be measured by this wear time sensor. If values are missing for a total of  $\geq 2$  hours during daytime, this day will be declared as non-eligible. In order to complete the data set of 2 weeks (10 working days) any non-eligible day will be replaced by daytime values in a pre-defined order, starting with the most recent day of the respective foregoing week (Figure 1). Weekend days are excluded from analysis.

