### **9.4 Data Sources**

Source documents are defined as original documents. The investigator will document patient data, including FSS, in his/her own patient files which will serve as source data for the study. Physical activity and sleep data will be collected by use of wrist-worn activity trackers (ActiGraph GT9X Link) which will be processed by device-specific software to obtain the physical activity and sleep-related variables for analysis.

All data collected by the activity tracker will be analyzed by the biostatistician at the end of the study. The data will not be seen by the investigators and patients at any time during data collection (between visit 1 and visit 5 (Figure 1: Study Activities)).

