## 11.1 Medical Complaints

### 11.1.1 Adverse Event Definition and Serious Adverse Event Categories

An adverse event (AE) is defined as any untoward medical occurrence in a patient, which does not necessarily have a causal relationship with their treatment. An AE can therefore be any unfavorable and unintended sign (including an abnormal laboratory finding), symptom, or disease temporally associated with the use of a medicinal product, whether or not the event is considered causally related to the use of the product.

Such an event can result from use of the drug as stipulated in the labeling, as well as from accidental or intentional overdose, drug abuse, or drug withdrawal. Any worsening of a pre-existing condition or illness is considered an AE. An AE can also derive from the medical device ActiGraph GT9X Link, which is used in this study. Minimal risks related to the Activity Tracker can be possible discomfort wearing the device around the clock and possible skin rash or skin irritation caused by the device.

Patient reported FSS questionnaire data are not considered a potential source of adverse reactions. However, participating sites should review the questionnaire data and if a possible product-related event (including a suspected adverse reaction) is noted, the Health Care Professional must determine whether the event is related to an AbbVie authorized product and if so, it should be reported to AbbVie. If an increase in the FSS score by  $\geq 1$  point is observed, the investigator must report this increased fatigue as an AE to AbbVie.

Patient derived activity tracker data are not considered a potential source of adverse reactions. Physicians are not able to see tracker data at any time. Thus, if a possible product-related event (including a suspected adverse reaction) is noted, activity tracker derived mean values of interest will be reported exclusively at the end of the study by the bio-statistician to the AbbVie PV team.

If an AE meets any of the following criteria, it is considered a serious adverse event (SAE):

---

Death of Patient:	An event that results in the death of a patient.
Life-Threatening:	An event that, in the opinion of the investigator, would have resulted in immediate fatality if medical intervention had not been taken. This does not include an event that would have been fatal if it had occurred in a more severe form.

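### Study withdrawal for under 3 weeks of tracker wear relies on data sites do not have before V5 and, where enforced, loses FSS and SVR12 results that do not need the tracker

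*Protocol*

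**What the plan says.** - **The rule.** Protocol 9.1.4 states that patients "who do not wear the activity tracker for at least 3 weeks before each visit will be withdrawn from the study". The consequence is withdrawal from the whole study, not loss of one tracker value.
- **How wear is measured.** Protocol 9.1.1: "Thus, patient compliance to the tracker will be measured by this wear time sensor".
- **Who can see it, and when.** Protocol 9.4: "The data will not be seen by the investigators and patients at any time during data collection". Protocol 11.1.1 adds: "Physicians are not able to see tracker data at any time". The patient keeps the device throughout, and 9.1.1 says "At the last visit, the investigator will collect the tracker and deliver it to the biostatistician".
- **What sites do at V2 to V5.** The visit table in 9.1.2 lists "Investigation of handling with the activity tracker", with no content defined. FSS and HCV viral load are taken at every visit.
- **Preparation phase.** Section 9.1.1 also ends participation if treatment is started "before the patient has worn the activity tracker for at least 4 weeks during the treatment preparation phase".
- **What the analysis needs.** Protocol 9.1.1 and SAP 3.1 require two weeks (10 working days) of eligible tracker data, with non-eligible days replaced from earlier weeks. A day is non-eligible if 2 or more daytime hours are missing. SAP 3.1 allows no other replacement.
- **Who is analysed.** SAP 5.2 analyses primary and secondary endpoints in the mITT, meaning ITT patients who take part in all five visits. It sets no wear criterion.

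**The concern.** The withdrawal decision falls due at each visit, but the designated measurement of wear does not reach anyone until the study is over for that patient. Neither document says who decides, on what evidence, or what counts as a week of wear. Two sites facing the same patient could decide differently.

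The consequence is also wider than the problem. Too little wear makes one tracker window less reliable, while withdrawal ends later FSS and HCV RNA collection, which do not use the tracker. Because of the five-visit mITT, FSS values already collected then leave the endpoint analyses too, and survive only in descriptive tables and ITT subgroup analyses. At stake are the size and make-up of the primary analysis set and the denominators for FSS and SVR12.

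**Working it through.** **1. The plan's own figure.** Inputs from Protocol 9.5: N = 100, effect size 0.29, two-sided one-sample t-test, alpha 0.05. Power is taken from the noncentral t distribution with n − 1 degrees of freedom and noncentrality 0.29 × √n. For n = 100 the noncentrality is 2.9 and power is 0.819, so the stated 80% is reproduced. The smallest n with at least 80% power is 96 (0.803); n = 95 gives 0.799. The calculation makes no allowance for withdrawals.

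**2. Three weeks against 10 working days.** Any 14 consecutive days contain 10 working days, and three weeks contain 15. A patient with at least two but under three weeks of wear can therefore supply the full 10 days if none is non-eligible, yet meets the withdrawal rule.

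**3. Total loss under full enforcement.** Four windows carry the rule (before V2, V3, V4 and V5). Neither document gives a failure rate, so p = 5% / 10% per window is an assumption.
- Fully correlated (the same patients fail every window): loss = p = 5% / 10%. This leaves 95 / 90 patients, with power 0.799 / 0.777.
- Independent: loss = 1 − (1 − p)^4. 1 − 0.95^4 = 0.185 and 1 − 0.90^4 = 0.344. About 81 / 66 patients remain, with power 0.732 / 0.641. The effect detectable with 80% power is 0.315 / 0.350.

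These figures count failures in the V5 window as lost to the primary analysis.

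**4. Primary endpoint if withdrawal were dropped.** The change from baseline to post-treatment week 12 needs only the V2 and V5 windows. With independent windows and the same p, 0.95^2 = 0.903 and 0.90^2 = 0.81 remain, so 90 / 81 patients and power 0.777 / 0.732. The avoidable cost in power is about 5 / 9 percentage points. Applying the same p to a 10-day criterion is cautious, since that criterion is easier to meet.

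**5. Avoidable SVR12 and V5 FSS losses.** A failure in the V5 window is established at V5, when FSS and HCV RNA are taken anyway. Only failures at V2, V3 or V4 cost these results: 1 − 0.95^3 = 0.143 and 1 − 0.90^3 = 0.271, or about 14 / 27 of 100 patients. If V2 failures leave before the first dose, they fall outside the ITT. The loss after V2 is then 0.95 × (1 − 0.95^2) = 0.093 and 0.90 × (1 − 0.90^2) = 0.171, or about 9 / 17.

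**6. If the rule is not enforced before V5.** The patient attends all five visits and stays in the mITT. The losses in steps 3 and 5 do not then arise, but the rule has no effect on the analysis as the SAP is written.

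**The case against.** **The rule can be applied.** A reader might infer that it is impossible to apply. The documents do not support that. Handling of the tracker is checked at V2 to V5, local staff are trained on the device and ActiLife 6, and gross non-wear can be found by asking. Tracker data handling is also said to be detailed in a Data Management Plan that is not available here. This stands: the rule is imprecise and open to uneven use, not inapplicable. No read-out before V5 is described.

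**The data loss presupposes enforcement.** Hidden data and full enforcement at every visit do not sit easily together. This also stands, so the figures above are conditional. A reader might put the SVR12 and FSS loss at 19 / 34 patients, the whole four-window total. That is too high, because it counts V5 failures whose V5 results exist, and it assumes independence although wear within a patient is plausibly correlated.

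**The 4-week and 3-week texts need not conflict.** The 4-week wording concerns early treatment start and can be read as a separate trigger. It overlaps with the 3-week rule only at V2, for a patient with 3 to under 4 weeks of wear. The documents do not settle which reading is meant. The 10-day figure is not a contradiction either: four weeks requested, three as a minimum and 10 working days analysed fit together, with 5 spare working days for replacement. What stands is that the minimum can remove patients whose data are usable.

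**Safety data.** A reader might infer that adverse event data are lost. Protocol 11.1.4 ties collection to the last dose, with no stated end at study withdrawal, so this is not shown.

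**Selection bias.** That non-wear goes with fatigue is plausible, but nothing in the documents establishes it. Protocol 9.9 already names failure to wear the device as a limitation.

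**Power.** Protocol 9.5 calls the study exploratory. That limits the weight of the power figures, although 9.7 does specify a test of the primary variable at 5%.

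**Conclusion.** The point holds in a limited form. The rule attaches a study-level consequence to a quantity sites cannot measure when the decision is due. Its effect depends on whether sites enforce it: if they do, patients leave all primary and secondary analyses, including those that need no tracker and some with usable tracker data; if they do not, low-wear patients stay in.

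Under the assumed 5% / 10% failure per window and full enforcement, total loss lies between 5% and 19% / 10% and 34%. The upper ends, and the power of about 73% / 64%, require independent windows. Avoidable SVR12 and V5 FSS losses are at most about 14 / 27 patients, and about 9 / 17 if V2 failures are never dosed. None of these rates comes from the documents. The stated sample-size figure itself is correct. This is a cheap improvement to who is analysed, not an error that invalidates the plan.

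**What to change.** - In Protocol 9.1.4, replace study withdrawal for tracker non-wear with an evaluability rule: a visit's tracker value is missing if the 10 eligible working days are not reached, judged by the biostatistician from the wear sensor after read-out.
- State that such patients remain under observation for FSS and HCV RNA, and add a sentence to SAP 5.2 including them in the FSS and SVR12 analyses.
- Reconcile the 4-week wording in 9.1.1 with the 3-week wording in 9.1.4, saying whether they are one requirement or two separate triggers.

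The cost is a short protocol amendment and one SAP sentence. There will be more visits with missing tracker values to report, and tracker and non-tracker endpoints will have different denominators. Patients without a usable V2 or V5 window would still be missing from the primary analysis, so the change reduces that loss but does not remove it.

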### **9.3.2 Secondary Variables**

- Change of Fatigue Severity Score (FSS) between baseline, during and after 12 weeks of treatment with 3D regimen
- Correlation between mean daytime physical activity and FSS at baseline, during and after 12 weeks of treatment with 3D regimen
- Proportion of patients achieving SVR12 after treatment with 3D regimen (defined as HCV RNA not detectable 12 weeks after the last actual dose of 3D regimen)
- Sleep efficiency at baseline, during and after 12 weeks of treatment with 3D regimen

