3.1 Handling of Missing Data

- Missing data from CRFs will be proven within the data collection in OpenClinica and clarified by queries to the monitoring.
- For tracker variables datasets of two eligible weeks (10 working days) are needed. If less than two eligible weeks are available, daytimes variables of previous weeks will be used.
- No other replacement of missing data will take place.

4 Objectives

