5.2 Analysis Populations (ITT and mITT)

The statistical analyses will be performed for the intention-to-treat population (ITT) and the modified ITT population (mITT) as well. The ITT consists of all documented patients of the overall population with treatment as intended to protocol and received study medication at least once. Additionally, mITT consists of all patients of the ITT which take part at all five visits. For ITT and mITT descriptive and safety parameters will be analyzed. Primary and secondary endpoints will be analyzed for mITT.

6 Statistical Methods

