6.3.3 Subgroup Analyses

According to the HEMATITE study protocol (version 1.0, 09/20/2016) „subgroup analyses will be provided for patients who achieve/do not achieve SVR12 after treatment with 3D regimen“. These analyses will be performed for ITT and mITT.

Daytime activity, FSS and sleep efficiency will be compared between following groups:

- Patients with Ribavirin vs. patients without Ribavirin at visit V2, V3, V4 and V5.
- Women vs. men at each visit.
- Patients with different fibrosis stages (F0, F1, F2 or F3) at each visit.
- Patients with different age categories (median split) at each visit.

Additionally for patients with GT1a vs. patients with GT1b FSS will be compared at each visit.

All statistical analyses will be performed by SPSS® for Windows, version 22.0.

7 Time table

The following temporary periods of time are planned:

| | |
|----------------------------------|------------------|
| Last patient out | April 2018 |
| Data input until | May 2018 |
| Cleanfile | June 2018 |
| Statistical analyses | Juli/August 2018 |
| Integrated Clinical Study Report | September 2018 |

Deviations from this plan because of unexpected occurrence are possible.

8 Planned tables for the statistical part

| Number | Items | Database/Variables |
|--|--|--|
| 1 Information to the study course | | |
| 1.1 | Enrolled/dropped out patients | Database 1 – Visit 1 (Day -28) |
| 1.2 | Study visits and study termination | Database 1 – Visit 1 (Day -28) – Visit 5 (Day 168, SVR12) |
| 1.3 | Patient eligibility criteria | Database 1 – Visit 1 (Day -28) |
| 2 Patients baseline characteristics | | |
| 2.1 | Demographics | Database 1 – Visit 1 (Day -28) |
| 2.2 | Medical history | Database 1 – Visit 1 (Day -28) |
| 2.3 | Fatigue severity scale (FSS) | Database 1 – Visit 1 (Day -28) |
| 2.4 | HCV history | Database 1 – Visit 1 (Day -28) |
| 2.5 | Vital signs | Database 1 – Visit 1 (Day -28) |
| 2.6 | Laboratory | Database 1 – Visit 1 (Day -28) |
| 2.7 | Smoking/alcohol status | Database 1 – Visit 1 (Day -28) |
| 2.8 | Activity tracker | Database 2 – Tracker data |
| 2.9 | Concomitant medication | Database 1 – Visit 1 (Day -28) |
| 3 Patients characteristics during study | | |
| 3.1 | Activity tracker | Database 2 – Tracker data |
| 3.2 | (S)AEs and concomitant medication | Database 1 – Visit 2 (Day 1) – Visit 5 (Day 168, SVR12) |
| 3.3 | Fatigue severity scale (FSS) | Database 1 – Visit 2 (Day 1) – Visit 5 (Day 168, SVR12) |

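### SVR12 is planned as a completer rate: treated patients without the fifth visit leave both numerator and denominator

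*Protocol*

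**What the plan says.** Protocol 9.1.1 states that "if 3D regimen is discontinued at the investigator's discretion, the patient will discontinue study participation". Section 9.1.4 repeats the rule and fixes where follow-up ends: for a decision to stop that was "taken before or during a routine clinic visit, this visit will be considered the last study visit". The same section withdraws patients with less than 3 weeks of tracker wear before a visit, and patients whose FSS is below 4 at Visit 2.

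The visit table in 9.1.2 places Visit 3 on Day 28, Visit 4 on Day 84 and the SVR12 visit, Visit 5, on Day 168. Section 9.3.2 defines SVR12 as "HCV RNA not detectable 12 weeks after the last actual dose of 3D regimen".

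SAP 5.2 defines the ITT set as "all documented patients of the overall population with treatment as intended to protocol and received study medication at least once", and adds that "mITT consists of all patients of the ITT which take part at all five visits". It then states: "Primary and secondary endpoints will be analyzed for mITT". On missing data, SAP 3.1 allows tracker days to be replaced from earlier weeks and then says: "No other replacement of missing data will take place". For the subgroups by SVR12 status, SAP 6.3.3 says: "These analyses will be performed for ITT and mITT".

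**The concern.** Read together, these rules make SVR12 conditional on reaching Visit 5. A patient who took 3D and stopped, or who was withdrawn over the tracker, is not counted as a failure or shown as unknown. The patient is simply absent from the proportion.

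This matters because few failures are expected. Protocol 7.0 cites SVR rates above 95%, so a handful of unmeasured patients can equal all the failures observed. A reader who sees an SVR12 proportion with a confidence interval may take it as the rate among patients who started 3D. The plan produces no such rate. An HCV RNA result from routine care after withdrawal has no place in the CRF under the current wording, and may not be recoverable later.

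**Working it through.** **1. The plan's own figure, to set precision aside.** Protocol 9.5 states 80% power for 100 patients, effect size 0.29, two-sided one-sample t-test at 5%. The noncentral t distribution with noncentrality 0.29 × √100 = 2.9 gives 81.9%, so the figure reproduces. With 95 patients the power is 79.9%. Losing a few patients costs little power. The question is who is counted.

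**2. Can an early stopper have a week 12 value?** Post-treatment week 12 is 12 × 7 = 84 days after the last dose. Assume that the next scheduled visit closes participation.
- Last dose on Day s before Visit 3: gap = 28 − s, at most 28 − 1 = 27 days.
- Last dose after Visit 3: gap = 84 − s. For a stop just after Visit 3 on Day 28 this is 84 − 28 = 56 days.

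The longest gap is 56 days against the 84 needed, so no early stopper has a study SVR12 value. Timed from the last actual dose, the measurement for a Day 28 stop would fall on Day 28 + 84 = Day 112.

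**3. Where does the patient go in the analysis?**
- Five-visit set: out, because there is no Visit 5.
- ITT: unclear, because the phrase about treatment as intended may or may not admit an early stopper. It makes no difference to SVR12, since ITT is given descriptive and safety parameters and the endpoints go to the five-visit set.
- Subgroups in ITT (SAP 6.3.3): a patient without an SVR12 result cannot be placed in either group.
- Imputation: none (SAP 3.1).

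**4. Who else is affected?** The five-visit rule also removes patients withdrawn for tracker non-wear, patients who miss any visit, and patients with FSS below 4 at Visit 2. The last group counts among the dosed only if 3D had already been started, as Visit 2 is the treatment-start visit.

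**5. Size.** Per 100 dosed, let k be the number without Visit 5 and r the SVR12 rate in completers. The all-dosed rate lies between (100 − k) × r, if all k failed, and (100 − k) × r + k, if all k responded. The width is k points. The documents give no value for k, so every k is an assumption. The value r = 95% is the floor of the figure in Protocol 7.0.

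| k | r | Lowest (%) | Highest (%) |
|---|---|---|---|
| 1 | 95% | 99 × 0.95 = 94.05 | 95.05 |
| 3 | 95% | 97 × 0.95 = 92.15 | 95.15 |
| 5 | 95% | 95 × 0.95 = 90.25 | 95.25 |
| 10 | 95% | 90 × 0.95 = 85.5 | 95.5 |
| 20 | 95% | 80 × 0.95 = 76.0 | 96.0 |
| 5 | 99% | 95 × 0.99 = 94.05 | 99.05 |

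At k = 5 and r = 95%, non-response among all dosed lies between 4.75% and 9.75%, against 5% in completers. The 5 unknown outcomes are about as many as the 4.75 expected failures among the 95 completers.

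**The case against.** The best defence is that the plan does not contradict itself. The SVR12 definition fixes a time point and names no denominator, and objective 8.2.1 speaks of patients newly starting 3D without saying all of them. A reader might infer that both promise an all-dosed analysis, but the text does not go that far. This stands: the completer set is a choice that needs a label and a companion figure.

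The completer set also fits the research question in 8.1, which asks about successful treatment. That stands for physical activity, and the five-visit analysis should stay. It is weaker for SVR12, which is itself the measure of success.

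The likely distortion may be modest. The study is exploratory and SVR12 is secondary. With 5 stoppers all counted as failures the rate is 90/100 = 90.0%, inside the exact 95% interval of 88.1% to 98.3% for 90/95 completers. This stands as a comment on size, though the interval covers sampling error and not unmeasured outcomes.

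The flowchart (SAP 6.1) and planned tables 1.1 and 1.2 will show attrition, so a reader could work out a crude bound. They will not show the outcomes of those who left, and 9.1.4 records the reason for withdrawal only if the patient offers it.

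Counting every missing result as failure would also score a patient who completed 3D but neglected the tracker as a virologic failure. That is a fair criticism of an unqualified failure count, and is why the missing must be split by reason and the rate called a lower bound.

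Two further inferences are tempting and not supported. One is that the primary activity change is biased: the documents give neither direction nor size for such a bias. The other is that safety reporting lapses at withdrawal: Protocol 11.1.4 runs it to at least 30 days after the last dose and does not end it when participation ends.

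**Conclusion.** The point holds for SVR12. If the plan is followed as written, SVR12 is the rate among patients who attend all five visits, and it says nothing about treated patients who do not. The all-dosed rate is undetermined by 1 percentage point per such patient per 100 dosed. The completer rate need not overstate it, because the unmeasured patients may have responded. How much this matters depends on how many patients are lost, which the documents do not say: about a point with one patient, 5 points with five, more if tracker withdrawals are common. The bounds assume that every five-visit patient has an HCV RNA result and that the completer rate is 95% (or 99% in the last row of the table).

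**What to change.** **SAP 5.2 and 6.3.2.** Keep the five-visit set for activity and for the question about successful treatment, and label its SVR12 as completer-based. Add SVR12 among all patients with at least one dose of 3D, with that set defined directly, because the ITT wording is ambiguous. Report two figures side by side: the rate with missing HCV RNA counted as failure, called a lower bound, and the rate among those with an observed result. Split the missing by reason: stopped 3D, tracker non-wear, FSS below 4 at Visit 2 if already dosed, missed visit or lost to follow-up.

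**Protocol 9.1.4.** End tracker participation for these patients, but with their consent still record in the CRF any HCV RNA routinely obtained 12 weeks after the actual last dose, and any new antiviral started before it. A result after a new antiviral is not counted as SVR12 to 3D.

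A re-timed study visit, an extra 4-week wear period, an adverse-event call and an all-dosed activity analysis are optional. The point does not depend on them.

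**Cost.** Some extra recording for the patients concerned and a few rows in one table. The SAP changes can be made before it is signed, which by its own terms happens before the database is closed. The real downside is that the lower-bound SVR12 could look noticeably less favourable if many patients are withdrawn, which is why the reasons must appear beside it.
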